### **Current Practice**

#### **Pre- operative**

- 2% Chlorhexidine bathing on the night before and morning of the operation
- Hair removed by clipping or other means of removal not more than one day prior to surgery
- Prophylactic antibiotic : Cefazolin 1g

#### **Principal Investigator:**

**Name (print      Signature: \_\_\_\_\_ Date: \_\_\_\_\_**

- Blood glucose assessment -Insulin infusion protocol shall be initiated on unit for patient's high blood glucose level >11.mmol (<200mg/Dl).

### **Intraoperative**

- 2% chlorhexidine and 70% alcohol based solution for skin preparation shall be used immediately prior to incision
- Appropriate prophylactic antibiotic shall be administered as per formulary
- Glycemic control shall be maintained at blood glucose levels of <11 mmol (<200mg/Dl)
- Patient Normothermia (> 36 centigrade) shall be monitored and maintained
- Antimicrobial re-dosing

### **Postoperative**

- Glycemic control shall be maintained at blood glucose levels of <11 mmol (<200mg/Dl)
- Prophylactic antimicrobials (if prescribed) shall be discontinued after 48 hours of surgery.
- Wound dressing assessed for dry and intact
- Wound dressing is Mepilex Foam dressing

***The current practice related to choice of wound dressing is the Mepilex foam boarder, however the institution is in the process of introducing the silver dressing as part of standard practice. The silver dressing has been approved by the products co-ordinator in the organisation***

***(Bundle of Care Interventions for the Prevention of Healthcare associated infections- CIPP 8834)***

#### **Length of stay:**

[figure not shown]
• Patients' typical length of stay:

- CSICU- 2.5-3.7 day
- CCU- 2
- CVT- 3 days

## **Description of intervention**

Intervention will consist of a replacement of the sterile plain postoperative dressing Mepilex border dressing (versatile five-layer all-in-one bordered foam dressing) with the sterile silver-impregnated dressing on 3 units: the CSICU, CVT. The dressing will be applied upon arrival in the CSICU directly on the incision after closure had been performed with sutures and/or staples and the Mepilex border. Dressings will be changed at seven (days) post-surgery (or sooner if oversaturated), and then changed whenever the dressing becomes saturated. Application of the dressing will be discontinued when the incision had epithelialized. There will be no changes in techniques or patient care, and no other changes of any kind (including surgeons) during the entire study period. Throughout the entire period of hospitalization, patients will be monitored for signs and symptoms of infection as per Center for Disease Control [CDC] guidelines ie is superficial, deep, organ space infection (CDC, 2010). Patients will be followed for signs and symptoms of SSIs up to one **month** following surgical intervention. Surgical site infections will be identified through assessment present in chart reviews, clinic visits, readmission to a hospital, laboratory culture surveillance, and telephone interviews at the one month period.

NB: The control group will have the Mepilex foam dressing. All other processes and care will be the same as the intervention group.

### **Data collection will include a check-list with:**

1. Demographic
2. Risk factors
3. Antimicrobial prophylaxis pre, intraoperative and post-operative.
4. Signs of wound infection following the CDC criteria
5. Type of dressing
6. Vital signs
7. Severity of illness using Parsonnet score

The checklist apart from the Parsonnet Score Checklist was developed by the research team.

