## Sampling technique

**Principal Investigator:**

**Name (print**      **Signature:** \_\_\_\_\_ **Date:** \_\_\_\_\_

The study will follow a randomised sampling approach. Randomisation will include: first patient transferred from OR to the CSICU will be part of the intervention group, second patient part of the control group. This sequence will be followed until the required sample size is reached.

Sample size will include:

In the year 2023 there were a total of 200 patients admitted for a cardiac surgical procedure requiring a mediastinal incision. Based on this population and sample size calculation- a total of 109 patients will be included – meeting the inclusion and exclusion criteria.

Ie 55 in the intervention group and 54 in the control group.

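### The protocol provides for no masked classification of surgical site infection, its only outcome, although the dressings look different and the arm follows from arrival order

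*Protocol*

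**What the plan says.** The Objectives section has one aim: to compare SSI rates between the silver dressing and the standard foam dressing.

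The arms are easy to tell apart. Description of intervention replaces the standard dressing "with the sterile silver-impregnated dressing on 3 units" and adds: "NB: The control group will have the Mepilex foam dressing". Under Sampling technique, allocation is by alternation: "first patient transferred from OR to the CSICU will be part of the intervention group, second patient part of the control group".

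On the outcome, Description of intervention states: "Throughout the entire period of hospitalization, patients will be monitored for signs and symptoms of infection", using the CDC categories of superficial, deep and organ-space infection. Follow-up runs to one month. SSIs are identified from chart reviews, clinic visits, readmissions, culture surveillance and "telephone interviews at the one month period".

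The data-collection list has "Signs of wound infection following the CDC criteria" as item 4 and "Type of dressing" as item 5. It adds: "The checklist apart from the Parsonnet Score Checklist was developed by the research team".

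These sections do not name the person who decides whether a patient has an SSI. They do not say whether that person or the telephone caller knows the arm, or how doubtful cases are settled.

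**The concern.** If the person who classifies a wound knows which dressing was used, belief about the dressing can affect the classification. The comparison then mixes the dressing's effect with the assessor's expectation (detection bias). A superficial infection called from signs and symptoms, or from a patient's account by telephone, leaves the most room for this.

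The Data analysis section plans a chi-square test and a logistic regression adjusted for patient characteristics. Neither can correct an outcome that was classified differently in the two arms. Few events are expected, so a small number of doubtful calls carries much of the estimate. Who classifies the outcome, and with what knowledge, is a matter of trial conduct that belongs in the protocol and is not something to leave to an analysis plan.

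**Working it through.** **Inputs.**
- Site SSI counts, from Current cardiac SSI rates: CABG 4/69 (2023) and 8/134 (2022); all cardiac 4/327 and 11/734.
- Arm sizes: 55 and 54 (Sampling technique); 75 and 75 (Abstract). Both are carried because the two sections disagree.
- Literature SSI rate: 10% (Background).
- Test: chi-square (Data analysis). Sidedness and alpha are not stated; two-sided 0.05 without continuity correction is assumed.
- The number of biased calls is an assumption throughout.

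**Step 1. Reproduce the site rates.** 4/69 = 5.8%, 8/134 = 5.97%, 4/327 = 1.2% and 11/734 = 1.5%, all as printed. Pooled over both years: CABG 12/203 = 5.9%; all cardiac 15/1061 = 1.4%.

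**Step 2. Expected SSIs per arm if silver has no effect** (arm size × rate).
- CABG rate: 55 × 12/203 = 3.25 and 54 × 12/203 = 3.19. With 75 per arm: 4.43.
- All-cardiac rate: 55 × 15/1061 = 0.78 and 54 × 15/1061 = 0.76. With 75 per arm: 1.06.
- At 10%: 5.5 and 5.4. With 75 per arm: 7.5.

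**Step 3. Effect on the estimate of one call moved each way** (one fewer under silver, one more under foam, CABG rate).
- 55/54: (2.25/55) / (4.19/54) = 0.0409/0.0776 = 0.53.
- 75/75: 3.43/5.43 = 0.63.

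**Step 4. Effect on the test.** For a and c SSIs in arms of n and m, with N = n + m:

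chi-square = N × [a(m − c) − c(n − a)]² / [n × m × (a + c) × (N − a − c)], 1 degree of freedom.

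| SSIs, silver vs foam | p at 55/54 | p at 75/75 |
|---|---|---|
| 0 vs 1 | 0.311 | 0.316 |
| 2 vs 4 | 0.388 | 0.405 |
| 0 vs 3 | 0.076 | 0.080 |
| 0 vs 4 | 0.040 | 0.043 |
| 1 vs 4 | 0.163 | 0.172 |

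For 0 vs 4 at 55/54: 109 × 220² / (55 × 54 × 4 × 105) = 4.23, p = 0.040. For 1 vs 4: 109 × 166² / (55 × 54 × 5 × 104) = 1.94, p = 0.163.

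One changed call therefore removes nominal significance. Going from 3 vs 3 to 0 vs 4 needs three fewer calls under silver and one more under foam, four in all.

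**Step 5. Systematic under-calling with no true effect.** Let the same true rate apply in both arms and let a share s of silver-arm SSIs go uncalled. The apparent risk ratio is then 1 − s. The rejection rate sums binomial probabilities over all tables with p < 0.05; tables with no events count as no rejection.

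| True rate | Arms | s = 0 | s = 0.25 | s = 0.5 |
|---|---|---|---|---|
| 5.8% | 55/54 | 5.3% | 6.7% | 11.2% |
| 10% | 55/54 | 5.4% | 8.1% | 18.1% |
| 5.8% | 75/75 | 5.1% | 6.6% | 12.9% |
| 10% | 75/75 | 5.1% | 8.6% | 21.8% |

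**The case against.** The strongest reply is that the protocol never says unmasked staff make the SSI call, and that the material where roles would be set out is not available here: the checklist appendix, the case report form and the table of job responsibilities. That stands as a limit. The supportable statement is that the available text provides for no masked classifier, not that the classifier is known to be unmasked. Knowledge of the arm is a strong inference from visibly different dressings and alternation.

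Four stronger readings are tempting and should not be drawn.
- **That whoever records the wound signs also records the dressing, because both are on one checklist.** The list names data items. It shows neither a form layout nor who completes each item, and its contents run from preoperative risk to one-month signs. Recording the arm is not itself a fault; the gap is that nothing separates the outcome call from it.
- **That the whole endpoint is subjective.** Cultures and readmissions are also sources, and CDC categories apply. Deep, organ-space and culture-positive cases leave less room for judgement than superficial ones.
- **That one biased call decides the result.** It can move the estimate a long way, but 2 vs 4 (p = 0.39) and 0 vs 1 (p = 0.31) are not significant. Much of this instability comes from the small sample, which is a separate problem.
- **That expectation is known to favour silver.** The Postoperative section reports that the hospital is introducing the silver dressing. It says nothing about what assessors believe.

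It is also fair that masked classification cannot undo bias already in ward observations, and that dated records would reveal the arm under alternation. Neither removes the point; both shape the fix.

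**Conclusion.** The point holds in this limited form. Followed as written, the plan leaves its only outcome open to detection bias that the planned adjustment cannot remove. Superficial SSI is the most exposed.

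The estimate is the more fragile quantity: one call each way can produce an apparent halving of risk with no true effect. Significance is easier to lose than to create, with one call against about four. Sustained under-calling of half the silver-arm SSIs would raise false rejection from about 5% to between 11% and 22% over the rates and arm sizes considered; under-calling of a quarter would raise it to about 7% to 9%.

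These sizes rest on the site and literature rates, an assumed two-sided 0.05 chi-square test, and assumed numbers of biased calls. The documents do not show that any biased call would occur. The conclusion is the same under either stated sample size. If the checklist appendix or the responsibilities table already provides for masked classification, a cross-reference in the main text would be enough.

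**What to change.** Amend Description of intervention and the data-collection list before enrolment:

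1. Record wound signs, culture results, readmission and treatment for infection on a separate outcome form that carries neither dressing type nor arm. Keep dressing type with the baseline and care data.
2. State that the final SSI yes/no and its depth under the CDC criteria are assigned from that form and from chart extracts. Remove dressing, arm, enrolment number and surgery order from both, and give days since surgery in place of calendar dates, because order reveals the arm under alternation.
3. Assign this task to an existing team member who neither allocates nor applies dressings.
4. State that the one-month caller follows a fixed script and is not shown the arm.
5. State that the masked classification is the SSI outcome that will be analysed.

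The cost is a re-laid-out form, a short protocol paragraph and some clerical time to prepare the extracts. No staff, visit or procedure is added. The remaining weakness is that ward observers still see the dressing, so masking is partial.

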### **Principal Investigator:**

**Name (print      Signature: \_\_\_\_\_      Date: \_\_\_\_\_**

The Modified Parsonnet Score checklist was developed as a preoperative score for adult cardiac surgery. The checklist is a validated, additive scoring system for predicting operative mortality risk in cardiac surgery (Parsonnet et al, 1989). See appendix 1; Checklist for Data collection

## **Data analysis**

Data analysis will be done using SAS software. Descriptive statistics will include frequencies and percentages. Comparisons between the 2 groups will include chi-square statistic for categorical variables and the t test for continuous variables. Logistic regression will be used to compare the risk of infection according to type of dressing and adjusting for patients' characteristics.

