### Methodology

A single center randomized control trial approach will be employed. Adult patients admitted post cardiac surgery with a sternotomy incision will be randomized into the intervention (n=75) or control group (n=75). Units will include the cardiac surgical intensive care unit, the coronary care unit and the cardiovascular telemetry unit. Intervention will include the use of a silver dressing on the sternotomy incisions and the donors sites where applicable. The control group will follow standard care processes. Data collection will include a checklist and the modified Parsonnet Score. Data analysis will include descriptive and inferential statistics.

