### Conclusion

The current rate of surgical site infection amongst cardiac surgical patients is 2.1 below the benchmark of 2.9 with an operational goal of 2.1.

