**BACKGROUND**

Worldwide, cardiovascular diseases are considered the primary contributor to global mortality. Annually, around 18 million individuals die from these diseases, with 85% of the fatalities attributed to heart attacks (Magnussen et al., 2023). The management of cardiac diseases involves either clinical or surgical approaches. Surgical interventions are chosen when they present a greater likelihood of cardiac rehabilitation compared to clinical treatments. As a result, surgeries are quite common and necessitate meticulous planning for nursing care during the postoperative phase. This planning should be based on evidence-based practices to guarantee the delivery of high-quality care to patients. Furthermore, it aims to proactively prevent complications associated with the procedure, including the occurrence of Surgical Site Infections (SSIs) (Pivoto et al., 2010; Vieira, Stocco, Ribeiro & Frantz, 2018).

Approximately 0.5% to 3% of patients undergoing surgery will experience infection at or adjacent to the surgical incision site. Compared with patients undergoing surgery who do not have a surgical site infection, those with a surgical site infection are hospitalized approximately 7 to 11 days longer (Seidelman et al, 2023). In addition prevalence of SSI in cardiac surgery was 10% (Maleknejad 2019). About 3% of patients who develop an SSI will die as a result(Awad 2012). Multiple studies confirm that SSIs are a complication with significant sequelae, such as longer hospitalisation, increased health costs, increased morbidity and mortality(Harder et al, 2013; Predin et al 2021).

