## **Research Setting and study population**

**King Faisal Specialist Hospital and Research Center- Jeddah**, a specialist referral and research center, which is a 390 bedded facility with three main domains of care namely Ambulatory Care (20 units), Nursing Speciality (13 departments), and Nursing General Services (10 departments). Patients admitted to Cardiac surgical intensive unit (CSICU), Coronary Care Unit (CCU) and Cardiovascular Telemetry- Adult (CVT Adult) Unit after cardiac surgery with a sternal wound.

In 2023 there was a total of 150 of adult cardiac patients admitted post cardiac surgery with a mediastinal incision.

[figure not shown]

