## **Principal Investigator:**

**Name (print      Signature: \_\_\_\_\_ Date: \_\_\_\_\_**

## Current cardiac SSI rates at KFSHRC-J

SSIs currently are a challenge amongst cardiac surgical patients. The operational benchmarking for SSIs is 2.9 with an operational goal of 2.1. and with the current numbers of SSIs the organisation was not able to outperform the benchmark. The below graph depicts the rates of SSI for the years 2022-2023.

Category	Benchmark	Operational Goal	Year to Date (2023)			Year to Date (2022)		
			No. of Procedures	No. of Infections	Rate	No. of Procedures	No. of Infections	Rate
CABG	2.9	2.1	69	4	5.8	134	8	5.97
All cardiac		2.1	327	4	1.2	734	11	1.5

Despite defined interventions to reduce SSIs such as the **Bundle of Care Interventions for the Prevention of Healthcare associated infections- CIPP 8834 - SSI Prevention Bundle**, the SSI rates for CABG and cardiac have soared in the latter part of 2023.

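### The only adjusted comparison of SSI is a logistic regression that, at the site's all-cardiac and abstract rates, often has no finite dressing odds ratio and at the CABG rate has too few events for several covariates

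*Protocol*

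**What the plan says.** The Data analysis section names SAS, descriptive frequencies, chi-square and t tests, and then the model: "Logistic regression will be used to compare the risk of infection according to type of dressing", with adjustment for patient characteristics. It neither lists nor limits those characteristics.

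The sample size appears in two forms. Sampling technique gives "Ie 55 in the intervention group and 54 in the control group". The Abstract has patients "randomized into the intervention (n=75) or control group (n=75". I carry both.

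The SSI rate also appears in several forms:
- The site table (Current cardiac SSI rates at KFSHRC-J) gives, for CABG, 4 infections in 69 procedures (2023) and 8 in 134 (2022). For all cardiac procedures it gives 4 in 327 and 11 in 734.
- The Abstract's conclusion says "The current rate of surgical site infection amongst cardiac surgical patients is 2.1".
- The Background cites a study in which "prevalence of SSI in cardiac surgery was 10" percent.

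The number of sternotomy patients in 2023 is stated twice, differently. Research Setting has "In 2023 there was a total of 150 of adult cardiac patients admitted post cardiac surgery with a mediastinal incision"; Sampling technique has "In the year 2023 there were a total of 200 patients admitted for a cardiac surgical procedure requiring a mediastinal incision".

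**The concern.** An ordinary logistic regression estimates the dressing effect from SSIs in both arms. If one arm has none, the likelihood keeps rising as the odds ratio moves towards 0 or infinity, so the estimate has no finite value. This happens even with dressing as the only term. If neither arm has an SSI, there is nothing to model. Each added covariate also draws on the same few events.

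With 109 or 150 patients and site rates of a few percent, this could happen often. What is at stake is the only adjusted estimate of the dressing effect. There is a second risk: if the fit fails after the data are seen, the method and covariates would be chosen after the event.

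**Working it through.** **Inputs.** Arms of 55/54 (Sampling technique) and 75/75 (Abstract). Control-arm SSI rate p2 from the protocol, one value at a time. Intervention rate p1 = p2 (no effect) or 0.48 × p2. The 0.48 is 9.2%/19.3%, from the general-surgery silver study cited in the Background. The protocol does not use it as a design input, so it is an assumption here.

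**Reproducing the site rates.** 4/69 = 5.80%, 8/134 = 5.97%, 4/327 = 1.22%, 11/734 = 1.50%. All agree with the table.

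**Which rate fits the enrolled patients?** Eligibility is scheduled cardiac surgery through a sternotomy, not CABG alone. The 2023 all-cardiac denominator of 327 exceeds the 150 or 200 sternotomy patients stated for that year, so 1.2% may be too low. The CABG and all-cardiac rows both show 4 infections in 2023, so all four were in CABG patients if CABG is part of the all-cardiac row. If all four had a sternotomy and the periods match, the rate is 4/200 = 2.0% to 4/150 = 2.67%. This is an assumption.

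**Formulas.** With a = (1−p1)^n1 and b = (1−p2)^n2:
- P(at least one arm has no SSI) = a + b − ab
- P(neither arm has an SSI) = ab
- Expected SSIs = n1·p1 + n2·p2

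Example, p2 = 2.1%, no effect, 55/54: a = 0.979^55 = 0.311, b = 0.979^54 = 0.318, ab = 0.099. The chance is a + b − ab = 0.530. Expected SSIs = 109 × 0.021 = 2.3.

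**Chance of at least one arm with no SSI** (no effect; risk ratio 0.48):

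| Control rate | 55/54 | 75/75 |
|---|---|---|
| 1.22% (all cardiac, 2023) | 76.1%; 86.6% | 63.7%; 78.5% |
| 1.50% (all cardiac, 2022) | 68.5%; 81.7% | 54.1%; 71.7% |
| 2.0% (4/200) | 55.5%; 72.7% | 39.1%; 59.8% |
| 2.1% (Abstract) | 53.0%; 70.9% | 36.6%; 57.6% |
| 2.67% (4/150) | 40.6%; 61.0% | 24.6%; 46.2% |
| 5.8% (CABG, 2023) | 7.6%; 24.3% | 2.3%; 13.0% |
| 5.97% (CABG, 2022) | 6.9%; 23.1% | 2.0%; 12.2% |
| 10% (literature) | 0.6%; 7.0% | 0.1%; 2.5% |

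**Chance of no SSI in either arm.** At 1.2-1.5%: 19-37% (55/54) and 10-26% (75/75). At 2.0-2.7%: 5-20% and 2-11%.

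**Expected SSIs in the whole trial** (risk ratio 0.48 to no effect):

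| Control rate | 109 patients | 150 patients |
|---|---|---|
| 1.2% to 1.5% | 1.0 to 1.6 | 1.4 to 2.2 |
| 2.0% to 2.7% | 1.6 to 2.9 | 2.2 to 4.0 |
| 5.8% to 5.97% | 4.7 to 6.5 | 6.4 to 9.0 |
| 10% | 8.0 to 10.9 | 11.1 to 15.0 |

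**Worked case, 0/55 against 2/54.** Maximum likelihood gives no finite odds ratio. For this two-by-two table, Firth's method equals adding one half to each cell: odds of 0.5/55.5 over odds of 2.5/52.5, which is 0.19, with profile-likelihood 95% CI 0.001 to 2.40. The risk difference is 0 − 2/54 = −3.7 points, Newcombe 95% CI −12.5 to 3.4.

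**No SSI in an arm.** The upper end of the exact two-sided 95% interval is one minus 0.025^(1/n): 6.5% for 0/55 and 4.8% for 0/75.

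**The case against.** **It belongs in the SAP.** Covariate lists and rules for separated data are commonly left to an SAP, and one may exist. The protocol does not name maximum likelihood, and Firth regression is still logistic regression, run in SAS. So their absence alone is no finding. What stands is that the protocol has already chosen the adjusted model and left the covariates open, and the usual form of that model does not suit the event counts its own tables imply.

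**A reader might infer that a zero arm is likely at every site rate.** The documents do not support that. CABG is also a site rate, and there the chance is 2-24%. It exceeds one half only if the control rate is below about 2.2% (no effect) or 3.4% (risk ratio 0.48) at 55/54, and below about 1.6% or 2.5% at 75/75.

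**The site rates may be too low for this trial.** This stands. The trial follows patients to one month through chart review, clinic visits, readmissions, cultures and telephone interviews. The protocol does not show that the site counts were collected that way. The Abstract also applies the dressing to donor sites, and the site section says that rates rose late in 2023. Each could raise the count.

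**A reader might infer that the chi-square test is a safe fallback.** It is not wholly so. It is undefined when neither arm has an SSI. With 1 to 4 SSIs in all, the expected SSI cells are about 0.5 to 2 per arm. Even at the CABG rate they are about 2.3 to 4.5, still below 5.

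**A reader might infer that all the risk factors listed in the Background enter the model.** The protocol does not say so; it sets no number.

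**The deeper problem is the sample size.** That is fair: it is not tied to an event rate. The fix below does not address that.

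**Conclusion.** The point holds with limits. At control rates of 1.2-2.7%, about 1 to 4 SSIs are expected. The chance that at least one arm has none is 41-87% at 55/54 and 25-79% at 75/75, and the usual fit then yields no finite adjusted odds ratio. At the CABG rate the failure is uncommon to moderate, but 5 to 9 SSIs cannot support several covariates. At 10% the zero-arm problem is at most 7%.

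This rests on reading the Abstract's 2.1 as a percentage, on the assumed 0.48, on the assumption behind 2.0-2.7%, and on independent patients with no loss to follow-up. Failure is not certain, and counts per arm can be reported in any case. The change is worth making before data are seen, but the trial's basic reporting does not depend on it.

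**What to change.** In Data analysis:
- Specify Firth penalised logistic regression (the FIRTH option in SAS PROC LOGISTIC) with profile-likelihood 95% confidence intervals.
- Limit the model to dressing and at most one pre-specified baseline covariate already collected. The Parsonnet score or age would serve; which one is for the investigators to decide.
- Report SSIs over patients in each arm, and the risk difference with a score (Newcombe) 95% confidence interval.
- State that if neither arm has an SSI, neither the model nor the chi-square test is computed, and each arm's exact two-sided 95% interval is reported instead.

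This takes a few sentences, the same SAS procedure and no new data. The price is less covariate adjustment and a slightly shrunken odds ratio. The adjusted estimate becomes computable whenever at least one SSI occurs. It stays very imprecise, as the worked case shows: the change adds no power and does not cure the low event count.
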